1.3.1 Selection of AUSTEDO Dose and Schedule of Administration

AUSTEDO is available in 6, 9 and 12 mg tablets. To allow a precise dose titration among study subjects, only 6 mg tablets will be used in the AUDYT trial. As this is an open label trial, all subjects will receive the study drug; there is no placebo arm. All subjects will be instructed to take AUSTEDO with food, and not to chew, crush or break the tablets. The trial will consist of 3 periods:

1. Ramp-up period: During this titration period, AUSTEDO will be started at 12 mg/day and increased up to 48 mg/day for most study subjects, up to 36 mg/day for study subjects receiving a strong CYP2D6 inhibitor, or up to the maximum, well-tolerated dose for those subjects unable to tolerate the maximum recommended dose of AUSTEDO. Dose-limiting toxicity will be defined in this protocol as the development of any of the following during the titration period: a) new or worsening depression, b) worsening of dystonic symptoms, c) QTc increase of >39 but <60 milliseconds from baseline, or d) any other sign or symptom that, at the PI's discretion, would preclude further safe titration of the study drug. AUSTEDO will be increased by 6 mg/week as recommended in the package insert,³ as shown in Table 2 below:

Table 2
Recommended AUSTEDO titration

	Total daily dose (mg)
Week 1	12
Week 2	18
Week 3	24
Week 4	30
Week 5	36
Week 6	42
Week 7	48

- 2. Maintenance period: Once on the maximum dose, subjects will complete 6 weeks of treatment on that dose, unless a side effects ensues. If so, it will remain at the investigator's discretion whether to discontinue the study drug, or to reduce the dose to a new, maximum, well-tolerated dose, on which the study subject will complete 6 weeks of treatment. Details on dose reduction will be discussed further elsewhere in this protocol.
- 3. Post treatment period: Following 6 weeks of treatment with AUSTEDO, the medication will be discontinued and a final safety evaluation will be performed once the subject has been 1 week off study drug.
- 2. TRIAL OBJECTIVES
- 2.1 Primary Objective

To explore the safety and tolerability of the daily oral administration of AUSTEDO in adult study subjects with dystonia.

- 2.2 Secondary Objectives
 - 1. To establish the degree of symptomatic effect of AUSTEDO as measured by the Clinical Global Impression of Improvement Scale (CGI-I) after 6 weeks of AUSTEDO 48 mg daily, or at the highest tolerated dose.

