2.3 Safety Outcome Assessments

The following assessments will establish the safety and tolerability of AUSTEDO during the AUDYT trial:

- Tolerability will be established by the proportion of study subjects able to titrate up to 48 mg/d (or up to 36 mg/d if receiving a strong CYP2D6 inhibitor) and able to complete the study at this dosage.
- Adverse events will be surveyed during all study Visits and during weekly telephone communications with the study subjects that will happen during the ramp-up period.
- AUSTEDO may prolong the QT interval. QT interval prolongation is associated with the development of tachyarrhythmias and Torsades de Pointes. To screen for the development of significant QT prolongation (defined as a corrected QT –Bazett– interval of 450 (458) milliseconds –or higher– in men or 460 (472) milliseconds –or higher– in women), a 12-lead electrocardiogram (ECG) will be performed during all scheduled study Visits, including the early termination Visit, if such a Visit happens. Should there be evidence of QT prolongation, it will remain at the investigator's discretion whether to discontinue the study drug, or to reduce the dose to a new, maximum, well-tolerated dose. A follow up ECG will be performed 1 week after the dose reduction (during an unscheduled Visit) to ensure the QTc is no longer significantly prolonged.
- A complete physical examination will be performed at the time of the initial and final study Visit, as well as during the early termination Visit, if applicable. Any and all changes in the examination happening during the trial will be recorded, and reported when appropriate.
- Vital Signs (including weight) will be measured and recorded during all scheduled study Visits, including the early termination Visit, if such a Visit happens. Any and all gross abnormalities or significant changes will be reported.
- Suicidal thoughts or actions are a possible side effect of AUSTEDO use. The Columbia Suicide
 Severity Rating Scale (C-SSRS) will be administered during all scheduled study Visits, including
 the early termination Visit, if such a Visit happens. Development of suicidality as determined by
 this instrument at any point during the trial will warrant the immediate discontinuation of the
 study drug, as well as psychiatric care as determined necessary by the investigator. Subjects
 with any signs or suicidality during Visit 1 as detected by the scale will be immediately excluded
 from participating in the trial.

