3.5.2.4 Dose Adjustment

Adjustments in the dose of AUSTEDO will be allowed throughout the study. If a reduction in the dose of AUSTEDO is required during the ramp-up period due to dose-limiting side effects, study subjects will be instructed to reduce the total daily AUSTEDO dose by 6 mg (1 tablet) every day until a new, maximum well-tolerated dose of AUSTEDO is established. A faster dose reduction will be allowed if deemed necessary by the investigator. Once this new dose is determined, the maintenance period will be considered initiated, and subjects will be instructed to complete Visit 3 and to remain on this dose for 6 weeks. Any side effects encountered will be recorded and reported as appropriate.

Dose-limiting toxicity will be defined in this protocol as the development of any of the following during the titration period: a) new or worsening depression, b) worsening of dystonic symptoms, c) QTc increase of >39 but <60 milliseconds from baseline, or d) any other sign or symptom that, at the PI's discretion, would preclude further safe titration of the study drug.

If a reduction in the dose of AUSTEDO is required during the maintenance period due to dose-limiting side effects, study subjects will be instructed to reduce the total daily AUSTEDO dose by 6 mg (1 tablet) every day until a new, maximum well-tolerated dose of AUSTEDO is established. A faster dose reduction will be allowed if deemed necessary by the investigator. Once this new dose is determined, subjects will be instructed to remain on this dose until the 6 weeks of the maintenance period are completed. A new maintenance period will NOT start every time a dose reduction is performed. Any side effects encountered will be recorded and reported as appropriate.

Increments in the total daily dose of AUSTEDO will not exceed 6 mg/week, as recommended by the package insert.³ Treatment interruptions will be discouraged unless necessary. In these cases, resuming AUSTEDO at the previous maintenance dose without titration will be allowed as long as the subject has been off study drug for 6 days or less. Subjects who require drug cessation for a week or more will be consider withdrawn from the trial, and will be asked to complete an early termination Visit.

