3.5.2.5 Subject Withdrawal

Subjects will be advised that they are free to withdraw from the study at any time. Reasons that subjects may be withdrawn from the study include the following:

• Subject discontinued study medication: according to the package insert,³ following treatment interruption of greater than one week, AUSTEDO therapy would need to be re-titrated when resumed, and, thus, subjects who require drug cessation for a week or more will be considered

withdrawn from the trial. For treatment interruption of less than one week, treatment can be resumed at the previous maintenance dose without titration, as per the package insert.³

- Subject consent is withdrawn
- QTc changes: A study subject will be asked to discontinue study drug if at any point during the trial he or she is found on ECG to have developed a QTc> 500 milliseconds or a QTc increase of >60 milliseconds from baseline.
- Sponsor decision, after discussion with the Investigator

If a subject is withdrawn from the study, all efforts will be made to complete the early termination Visit that includes efficacy assessments and safety follow-up. In addition, women of childbearing potential will have a pregnancy test performed at the early termination Visit. All information, including the reason for withdrawal, will be reported. For subjects who are lost to follow-up, three recorded attempts will be made to contact the subject for follow-up information, including reason for discontinuation and follow-up of AEs. Subjects who withdraw from the study will not be replaced.

- 3.6 Study Procedures and Assessments
- 3.6.1 Safety assessments
- 3.6.1.1 Adverse Events

During the study, the Investigator or study site personnel will be responsible for querying and recording adverse events (AEs) and serious adverse events (SAEs). In this study AEs and SAEs will be reported from the time of study drug administration until Visit 5 or death, whichever occurs first.

An adverse event (AE) is any untoward medical occurrence that occurs in conjunction with the use of a medicinal product in humans, whether or not considered to have a causal relationship to the medicinal product. According to the package insert,³ adverse reactions experienced by at least 4% of subjects on AUSTEDO and with a greater incidence than on placebo include somnolence, diarrhea, dry mouth, fatigue, urinary tract infection, insomnia, anxiety, constipation and contusion.

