3.6.1.2 ECG

AUSTEDO may prolong the QT interval. QT interval prolongation is associated with the development of tachyarrhythmias and Torsades de Pointes. To screen for the development of significant QT

prolongation (defined as a corrected QT –Bazett– interval of 450 (458) milliseconds in men or 460 (472) milliseconds in women), a 12-lead electrocardiogram (ECG) will be performed during all scheduled study Visits, including the early termination Visit, if such a Visit happens. Should there be evidence of QT prolongation, it will remain at the investigator's discretion to either discontinue the study drug, or to reduce the dose to a new, maximum, well-tolerated dose. A follow up ECG will be performed 1 week after the dose reduction (during an unscheduled Visit) to ensure the QT prolongation is no longer significant.

However, a study subject will be asked to discontinue study drug if at any point during the trial he or she is found on ECG to have developed a QTc> 500 milliseconds or a QTc increase of >60 milliseconds from baseline. Study subjects will be asked to come in for an Early Termination Visit within 3 business days of study drug discontinuation.

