Table 6 below shows a list of medications that are known to prolong the QTc. Subjects taking these medication will be allowed to participate in the trial as long as their ECG during visit 1 (and while already on one or more of these drugs at steady state) shows no QTc prolongation. Any evidence of QTc prolongation during subsequent ECGs will require an adjustment in the AUSTEDO dose as detailed elsewhere. The introduction of these medications will not be allowed for the duration of the trial. If it is determined that a subject requires one of these medications during their participation in the trial, AUSTEDO will be stopped and the subject will be considered withdrawn from the trial.

Table 6 Drugs causing QTc prolongation
Moxifloxacin
Quinidine
Procainamide
Amiodarone
Sotalol

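### The dose-limiting QTc rise (>39 but <60 ms) counts only during titration; at full dose the same rise below the absolute limit meets no numeric rule, only investigator discretion

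*Combined protocol and SAP*

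**What the plan says.** Sections 1.3.1, 3.1 and 3.5.2.4 each define dose-limiting toxicity as "any of the following during the titration period". Item (c) of that list is a "QTc increase of >39 but <60 milliseconds from baseline".

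ECGs are taken at the scheduled visits (2.3, 3.1). Visit 2 is 5-9 days after the first dose (3.5.1.2), and the rest of the ramp-up is followed by weekly telephone calls. Visit 3 is in week 7, or week 5 with a strong CYP2D6 inhibitor (3.5.1.3). The Synopsis and 3.4.3 place it at the start of maintenance.

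These provisions apply at Visit 3:

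- **Stopping rule** (3.5.2.5, 3.6.1.2, 5.6): "QTc> 500 milliseconds or a QTc increase of >60 milliseconds from baseline".
- **Absolute limit** (2.3, 3.6.1.2): 450 ms in men and 460 ms in women (458 and 472 in brackets), with reduction or discontinuation left to the investigator.
- **Co-medication text** (4.8): "Any evidence of QTc prolongation during subsequent ECGs will require an adjustment in the AUSTEDO dose".
- **Maintenance dosing** (1.3.1 item 2): six weeks at the dose reached "unless a side effects ensues", in which case the investigator decides.
- **Maintenance reduction** (3.5.2.4): "If a reduction in the dose of AUSTEDO is required during the maintenance period due to dose-limiting side effects", step down by 6 mg a day. No QTc figure is attached.

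**The concern.** The protocol chose a change-from-baseline threshold at which the dose should stop rising. By schedule, that threshold is tested only at the two lowest doses and not at the highest. A 50 ms rise at Visit 2 is dose-limiting by rule. The same rise at Visit 3 is not, provided QTc stays under the absolute limit.

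Section 4.1.4 reports linear dose dependence of exposure to the active metabolites over the doses studied. Section 4.1.3 reports a mean QTc rise of about 4.5 ms (90% CI 2.4 to 6.5) after a single 24 mg dose and says that higher exposures have not been evaluated. Section 5.1.1.2 names users of strong CYP2D6 inhibitors as at risk of relevant prolongation. What is at stake is subject safety in a trial whose primary objective is safety and tolerability: a subject could stay at maximum dose for five to six weeks after a rise that the protocol would have acted on earlier.

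**Working it through.** The plan has no figure of its own to reproduce here. The check is arithmetic on the schedule and the thresholds.

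**1. Dose at each ECG** (Tables 3 and 4: 12 mg/day in week 1, then +6 mg/day each week up to the cap).
- Visit 2, days 5-9: 12 mg/day in week 1, 18 mg/day in week 2.
- Visit 3: week 7 at 48 mg/day, or week 5 at 36 mg/day with a strong inhibitor.
- Dose ratio, Visit 3 to Visit 2: 48/18 = 2.7 to 48/12 = 4.0; with an inhibitor, 36/18 = 2.0 to 36/12 = 3.0.

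These doses are for subjects who reach their maximum. Those limited earlier have Visit 3 at a lower dose.

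**2. Who escapes every numeric rule at Visit 3.** The condition is baseline + rise < absolute limit, with a rise of at most 60 ms.

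| Rise | Men, baseline below | Women, baseline below |
|---|---|---|
| 40 ms | 450 - 40 = 410 (bracketed limit: 418) | 460 - 40 = 420 (432) |
| 60 ms | 450 - 60 = 390 (398) | 460 - 60 = 400 (412) |

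All these baselines are eligible under exclusion criterion 13. Example: a man with baseline 395 ms and Visit 3 QTc 445 ms has risen 50 ms. He is under 450, under 500 and not above a 60 ms rise, so no rule fires.

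The baseline distribution is not given. Assuming a normal baseline with mean 390-420 ms and SD 15-25 ms, 26-91% of eligible men lie below 410 ms and 50-98% of eligible women below 420 ms. The gap is not confined to unusual baselines.

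**3. Time to the next scheduled ECG** (first dose = day 0).
- 48 mg/day: week 7 is days 42-48 and week 12 is days 77-83. Interval 77 - 48 = 29 to 83 - 42 = 41 days. Dosing left: 84 - 48 = 36 to 84 - 42 = 42 days.
- 36 mg/day: week 5 is days 28-34 and week 10 is days 63-69. Interval 63 - 34 = 29 to 69 - 28 = 41 days. Dosing left: 70 - 34 = 36 to 70 - 28 = 42 days.

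**4. Boundary.** The band ends at <60 ms and the stop begins at >60 ms, so exactly 60 ms meets neither.

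**5. Frequency, as an assumption only.** No SD of QTc change is in the documents. At 48 mg/day each dose is four 6 mg tablets, or 24 mg, the same dose that gave 4.5 ms. With a half-life of 9-10 hours (4.1.4) and an assumed 12-hour interval, accumulation is 1/(1 - 2^(-12/9)) = 1.66 to 1/(1 - 2^(-12/10)) = 1.77, about 1.7. If effect is proportional to exposure, the mean is 4.5 × 1.7, about 7.7 ms. For a normal change, P(39 < rise <= 60) is:
- SD 10 ms: about 0.09% per ECG, or 0.013 of 15 subjects.
- SD 20 ms: about 5.4% per ECG, or 0.81 of 15 subjects.

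This applies to subjects without a strong inhibitor. Within these assumptions it overstates the gap, because some subjects in the band would also reach the absolute limit.

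**The case against.** The strongest reply is that only a mandatory number is missing. The investigator has the Visit 3 ECG in hand, may reduce or stop for any side effect in maintenance (1.3.1 item 2), may adjust the dose throughout (3.5.2.4) and may call an unscheduled visit (3.5.2.3). The hard stops apply at every ECG. This stands, and it limits the seriousness. It does not explain why a number is needed at 12-18 mg/day and discretion is enough at 48.

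A second reply is that the maintenance paragraph of 3.5.2.4 follows directly on the definition and uses the same dose-limiting language, so a site could carry criterion (c) over. Table 2, placed under the ramp-up item, also lists week 7. But the definition is expressly confined to titration, and the Synopsis, 3.4.3 and 3.5.1.3 put week 7 in maintenance. If carry-over was meant, the text should say so. The 4.8 sentence does not fill the gap either: it sits in the paragraph on QT-prolonging co-medication, and prolongation is defined only by absolute value.

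Third, a titration rule has a purpose of its own, since no escalation follows Visit 3. That is fair, but 36-42 days at maximum dose do follow.

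Fourth, a mandatory reduction on one unconfirmed ECG would be costly, because it counts as a primary endpoint failure. This stands, and the remedy should require confirmation first.

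**Conclusion.** The point holds on the text. In maintenance a rise of 40-60 ms below the absolute limit meets no numeric rule, at 2-4 times the dose at which the rule is tested by schedule. The exact 60 ms omission is a minor drafting error. The change is worth making because it is cheap and concerns safety at the highest dose; it closes a gap in a rule that discretion partly covers.

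Three stronger readings are not supported:

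- **That full-dose subjects have no QTc protection.** The stops, the absolute limit and investigator discretion all apply.
- **That a case among the 15 is likely.** Taking three times the 24 mg effect (13.5 ms) with SD 20 ms for every subject gives 9.1% per ECG and 1 - (1 - 0.091)^15 = 76% for at least one. But a threefold exposure is documented only with strong CYP2D6 inhibitors (4.8), who are capped at 18 mg per dose, and the SD is assumed. The 0.09% to 5.4% above is likewise an illustration and does not bear on the textual point.
- **That the primary endpoint is biased.** Nothing in the documents shows this.

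**What to change.** 1. In 1.3.1, 3.1 and 3.5.2.4, apply criterion (c) at any on-treatment ECG and make the band >39 to <=60 ms.
2. At Visit 3, or at an unscheduled ECG in maintenance, confirm a rise in the band by a prompt repeat ECG at an unscheduled visit, which 3.5.2.3 already allows. If confirmed, reduce the dose as 3.5.2.4 describes and do the existing one-week follow-up ECG.
3. Amend 2.3 and 3.6.1.2 so that the follow-up ECG also checks that the rise is 39 ms or less. The present aims, "to ensure the QTc is no longer significantly prolonged" and "to ensure the QT prolongation is no longer significant", are already met by a subject under the absolute limit.
4. At Visit 4, record the rise, end dosing as planned and recheck at Visit 5.
5. Leave the >60 ms and >500 ms stops unchanged at every ECG.

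The cost is wording in five sections (1.3.1, 3.1, 3.5.2.4, 2.3, 3.6.1.2) and no new scheduled ECG. Some subjects will need an unscheduled repeat ECG, and a few a dose reduction. Under 3.7.1.1 a subject reduced at Visit 3 has not completed at the maximum dose, so each one moves the primary proportion by 1/15 = 6.7 points.

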2.3 Safety Outcome Assessments

The following assessments will establish the safety and tolerability of AUSTEDO during the AUDYT trial:

- Tolerability will be established by the proportion of study subjects able to titrate up to 48 mg/d (or up to 36 mg/d if receiving a strong CYP2D6 inhibitor) and able to complete the study at this dosage.
- Adverse events will be surveyed during all study Visits and during weekly telephone communications with the study subjects that will happen during the ramp-up period.
- AUSTEDO may prolong the QT interval. QT interval prolongation is associated with the development of tachyarrhythmias and Torsades de Pointes. To screen for the development of significant QT prolongation (defined as a corrected QT –Bazett– interval of 450 (458) milliseconds –or higher– in men or 460 (472) milliseconds –or higher– in women), a 12-lead electrocardiogram (ECG) will be performed during all scheduled study Visits, including the early termination Visit, if such a Visit happens. Should there be evidence of QT prolongation, it will remain at the investigator's discretion whether to discontinue the study drug, or to reduce the dose to a new, maximum, well-tolerated dose. A follow up ECG will be performed 1 week after the dose reduction (during an unscheduled Visit) to ensure the QTc is no longer significantly prolonged.
- A complete physical examination will be performed at the time of the initial and final study Visit, as well as during the early termination Visit, if applicable. Any and all changes in the examination happening during the trial will be recorded, and reported when appropriate.
- Vital Signs (including weight) will be measured and recorded during all scheduled study Visits, including the early termination Visit, if such a Visit happens. Any and all gross abnormalities or significant changes will be reported.
- Suicidal thoughts or actions are a possible side effect of AUSTEDO use. The Columbia Suicide
 Severity Rating Scale (C-SSRS) will be administered during all scheduled study Visits, including
 the early termination Visit, if such a Visit happens. Development of suicidality as determined by
 this instrument at any point during the trial will warrant the immediate discontinuation of the
 study drug, as well as psychiatric care as determined necessary by the investigator. Subjects
 with any signs or suicidality during Visit 1 as detected by the scale will be immediately excluded
 from participating in the trial.
- Somnolence is a possible side effect of AUSTEDO use. The Stanford Sleepiness Scale (SSS) will be administered during all scheduled study Visits, including the early termination Visit, if such a Visit happens. Should this side effect develop, the investigator will decided whether to continue AUSTEDO at the current dose, to discontinue the study drug, or to reduce the dose to a new, maximum, well-tolerated dose.
- To assess the impact AUSTEDO may have on cognitive function, if any, the Mini Mental State Examination (MMSE) will be administered during Visits 1, 4 and during the early termination Visit, if such a Visit happens. It will remain at the investigator's discretion to either discontinue the study drug, or to reduce the dose to a new, maximum, well-tolerated dose if clinically-

- significant, new-onset cognitive impairment is identified at any point during the course of the trial, even if detected during Visits during which the MMSE is not administered.
- To screen for the development of drug-induced parkinsonism, a possible side effect of AUSTEDO use, the MDS-UPDRS (Part III) will be administered during Visits 1, 4 and during the early termination Visit, if such a Visit happens. It will remain at the investigator's discretion to either discontinue the study drug, or to reduce the dose to a new, maximum, well-tolerated dose if clinically-significant, new-onset drug-induced parkinsonism is identified at any point during the course of the trial, even if detected during Visits during which the MDS-UPDRS (Part III) is not administered.

